[name] will recruit from local early intervention providers (including Birth to Three Developmental Services, A Step Ahead in Pierce County, and Tacoma Learning Center), Mary Bridge Children's Hospital, the Children's Therapy Unit, and from Washington Pediatric Special Interest Group. [name] has successfully recruited subjects from these sites previously.

No problems with recruitment of study participants are anticipated due to each investigator's connections in their local medical community. If one of the sites should fall short of qualified children, more children could be covered at one of the other sites. Drop-out rates are expected to be low due to the home-based nature of the study. All of the outcome measures as well as the intervention will be conducted at the children's homes. It is possible that a young child might fall sick for any of the planned visits by the PIs, or might not fully participate in one of the visits for other reasons. In this event, the PI will reschedule a repeat visit within a few days of the original visit to collect the data.

Between the three sites, twelve children will receive high-intensity treadmill training and twelve children will receive low-intensity treadmill training. Due to the stringent inclusion and exclusion criteria, the children in the two groups are expected to show no significant between-group differences at baseline. In [name] previous study on home-based treadmill training, group allocation using the same criteria led to two groups with no significant differences regarding age and developmental skills.¹⁷

Power Analysis

Power analysis was conducted to determine a sample size based on developmental data and based on StepWatch data.

To examine the optimal dosing for walking attainment, a projected sample size of 18 subjects (9 per group) at 95% power was calculated from Peabody Developmental Motor Scales-2 Locomotion subscale change scores from [name] previous home-based treadmill training study (n=12; GMFCS levels I and II; ages 15-32 months)¹⁷. An additional 6 subjects will be added to strengthen the study design and allow for possible attrition, leading to a total number of 24 subjects.

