To assure sufficient power to assess the effects of treadmill training on overall walking activity, a proposed sample size of 12 per group would have 80% power to detect a 3000 stride/day difference in treatment intensity as measured with the StepWatch monitor. This is based on [name] cross-sectional StepWatch average stride/day data from 17 youth with CP ages 2-3 years where the mean difference between GMFCS level I and II was 3000 strides.¹⁸

[figure not shown]

Fig. 4. Power analysis for sample size ($\alpha = 0.0$; Power= 0.95; Effect size=1.87; Sample size=18)

Methodology

Approval from the University Institutional Review Board was submitted on July 10, 2014 and approved on July 29, 2014 by the lead institution at California State University, Sacramento. A cooperative agreement will be put in place prior to study onset with the other institutions (please see attached). Due to the children's young age, written informed consent will be obtained from the parents. Parents will be asked to commit to a 6-week stretch uninterrupted by vacations or breaks. Study participation will be discussed and scheduled carefully with the families to allow for 6 weeks of uninterrupted intervention period. Due to the nature of the home-based administration of the intervention by parents and caregivers, high adherence to the study protocol is expected. Investigators will schedule weekly home visits and all assessments at a mutually agreed upon time that is convenient for the families.

After consenting to study participation, the parents for each child will fill out a parent questionnaire containing demographic and health information about their child. A physician form will also be signed prior to study onset to seek medical clearance for the child for the intervention. Group allocation will be determined by blinded drawing from a hat until each of the three study sites has reached a total of 4 children in each group. In the unlikely event that one site might have difficulty with subject recruitment, additional children will be enrolled at another study site.

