A portable pediatric treadmill equipped with a non-resettable minute timer and adjustable handle bars will be provided to the families at no charge for the duration of the intervention period. The treadmill handles will be adjusted to the child's correct height. There will be a one-week training period for each child to familiarize the family with the treadmill intervention. This will be achieved by demonstration by the PI, followed by correct execution by the parent. Should a parent be unable to perform the treadmill training safely, additional training will be provided. In the unlikely event that a parent should be unable to learn to perform the intervention safely, the PIs reserve the right to remove the treadmill from the home and cease the child's study participation. In this case, this subject will be reported as a drop-out and the data will be excluded.

In the improbable event of technical problems with one of the treadmills, [name] will substitute the treadmill with one that is currently housed and used in a community program at the University. This back-up treadmill could be shipped overnight to another site if need be.

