Each child will be tested at pre-intervention, post-intervention, at 1-month and at 4-months following the intervention. The testing will be scheduled at a mutually agreed-upon and convenient time with the family at their home. The children will undergo 6 weeks of treadmill training in their homes administered by a parent or primary caregiver who has been trained to safely provide the intervention. Weekly visits will be conducted by the researchers to adjust the treadmill speed and make any needed corrections to the parents' technique. The treadmill speed will be increased each week as tolerated by the child. The speed will not exceed 0.6 meter/second. In a previous study by [name] using a similar sample and treadmill protocol, the average starting speed was 0.1 meters/second and increased to an average of 0.25 meter/second over the duration of 6 weeks.¹⁷ Children assigned to the high-intensity group will walk on the treadmill 5 days/week, twice daily for 10-20 min for 6 weeks. Children in the low-intensity group will walk on the treadmill 2 days/week, once daily for 10-20 minutes for 6 weeks. The children will be motivated during the treadmill walk with a child-friendly video shown on a television, computer, or tablet. If uninterested, children will be encouraged with other motivational toys suggested by the parents. These motivational methods led to high adherence in [name] previous study on a similar sample of young children with CP.¹⁷

There is a possibility that a child might miss a training session due to sickness or other family obligations. The parents will be encouraged to make up a missed session on a different day. In the low-intensity group, the children have 5 days/week without treadmill training that could be used as make-up days. In the high-intensity group, the children have 2 days/week without treadmill training that could be used as make-up days. If a missed day cannot be made up, the parents will be encouraged to attempt to

train for the maximal 20 minutes for each treadmill walk in order to make up some of the missed minutes during other walks. The parents will document the minutes walked and the speed of each treadmill walk on a paper flow chart that is provided to them by the PIs.

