The study protocol was submitted to the Institutional Review Board (IRB) at California State University, Sacramento, on July 10, 2014 and approved on July 29, 2014 (IRB protocol #13-14-156). In addition, the consent form, permission to be videotaped, parent questionnaire and physician form for the study were all approved by the IRB. Once the grant is received, a cooperative agreement form will be signed by the two participating universities before the study commences.

Selection of the families will be made by judgment of the PI. Factors will include parental ability to correctly perform the treadmill training and safety during treadmill training sessions. The PIs reserve the right to terminate participation in the study if parents are unable to adhere to the agreed-upon treatment regimen, or display incorrect or unsafe technique during training. Any adverse events will be reported to the IRB. Because this intervention is conventionally used in physical therapy practice, adverse events are not anticipated. A small incentive will be offered to families to encourage participation. The families have the right to terminate participation in the study without any reason or penalty.

The study will be conducted in the children's homes. The last names of the children will not be used when other persons are present in the area. The PIs will abide by Health Insurance Portability and Accountability Act (HIPAA) regulations on children's privacy. When reporting results, only ages, diagnosis, functional level and gender of children will be reported. Photographs and/or video clips of children might be used when reporting results, but only with written permission of the parents/guardians. No mention of exact geographical location will be made.

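### A child removed because the parent cannot train safely has the data excluded, later removals have no data rule, and no analysis as allocated is stated

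*Combined protocol and SAP*

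**What the plan says.** The Methodology section describes consent, forms and medical clearance, and then the draw: "Group allocation will be determined by blinded drawing from a hat". It then turns to the treadmill at home: "There will be a one-week training period for each child to familiarize the family with the treadmill intervention". A parent who cannot train safely is offered more training. If that fails, the PIs may take the treadmill away and end the child's participation, in which case "this subject will be reported as a drop-out and the data will be excluded".

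Human Subjects contains two further statements. One is about entry: "Selection of the families will be made by judgment of the PI", with the parent's ability to do the training among the factors. The other is about removal: the PIs may "terminate participation in the study if parents are unable to adhere to the agreed-upon treatment regimen", or for incorrect or unsafe technique. It does not say what happens to these children's data or whether their later assessments go ahead.

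Data Analysis gives the tests and alpha 0.05. It names no analysis population and no method for missing data. Power Analysis deals with loss only by numbers: "An additional 6 subjects will be added to strengthen the study design and allow for possible attrition".

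**The concern.** Randomisation makes the arms comparable only if the children compared are those who were allocated. A rule that deletes a child after allocation, or silence that permits it, gives up that protection when the reason for removal depends on the arm and is related to outcome.

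The safe-technique rule need not differ by arm, since every family has the same training week. Removal for non-adherence is different, because the regimens differ. Missed sessions are also easier to recover in one arm: "In the low-intensity group, the children have 5 days/week without treadmill training that could be used as make-up days", against "In the high-intensity group, the children have 2 days/week without treadmill training that could be used as make-up days". The PIs who may remove a child also supervise the training weekly, and only the assessor scoring the GMFM and PDMS-2 videos is described as blinded. With 12 children per arm, one removal is 8% of an arm (1/12).

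**Working it through.** **1. The plan's own figure.** Power Analysis gives effect size 1.87, power 0.95 and 9 per group. A two-sample t-test at two-sided 0.05 (sidedness assumed) has power 0.935 at 8 per group and 0.961 at 9, so N = 18 reproduces. The 6 extra children are 6/24 = 25% of the total. The sample size is not at fault, but extra children protect power, not comparability.

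**2. Load by arm (Interventions; Methodology).** High: 5 days × 2 walks × 6 weeks = 60 sessions. Low: 2 × 1 × 6 = 12.

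**3. Timing of each rule.**

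| Rule | Before or after the draw? | Data rule |
|---|---|---|
| Parent cannot learn safe training (Methodology) | Described after it; order not stated | Excluded |
| Non-adherence to regimen (Human Subjects) | After; a regimen must first be assigned | None |
| Incorrect or unsafe technique (Human Subjects) | Not stated | None; the unsafe part overlaps the first row |

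**4. Size, as an illustration.** The documents give no removal counts or correlations, so all of these are assumptions: no true effect; 12 v 12; k children removed from the high-intensity arm only; their data excluded; the k removed have the lowest scores on a removal tendency that correlates ρ with outcome. The expected shift in the high-arm mean, in SD units, is

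shift = ρ × (sum of the k largest expected normal order statistics for n = 12) / (12 − k).

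The order statistics are 1.629, 1.116 and 0.793. At ρ = 0.5:

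- k = 1: 0.5 × 1.629 / 11 = 0.074
- k = 2: 0.5 × 2.745 / 10 = 0.137
- k = 3: 0.5 × 3.538 / 9 = 0.197

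Against the planned effect size of 1.87 (if in the same SD units) these are 4.0%, 7.3% and 10.5%. For ρ from 0.3 to 0.7 the shifts are 0.04-0.10, 0.08-0.19 and 0.12-0.28 SD.

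Simulating the same setting with a pooled two-sided t-test at 0.05 (4,000,000 trials each) gives type I error of 5.5%, 6.4% and 7.4%. With the mean shift subtracted it is still about 5.2%, which is an effect of trimming and not of bias. At ρ = 0 there is no shift and the error is 5.0%. Equal removal from both arms at ρ = 0.5 gives no shift and 5.4-5.7%.

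**5. Does deleting the exclusion help by itself?** Not if the removed child has only a baseline and the analysis ignores it. Baseline adjustment may help, by an amount that depends on what drives removal. Let r be the baseline-outcome correlation (assumed) and take k = 2, ρ = 0.5:

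- Removal driven by the outcome: the baseline means shift by r times the outcome shift and the slope is about r, so about 1 − r² of the bias remains. For r = 0.7, 0.51 × 0.137 = 0.07 SD; for r = 0.5, 0.75 × 0.137 = 0.10 SD. Simulation gives 0.07 and 0.10.
- Removal driven by baseline: simulation leaves about 0.00 SD.
- Removal driven by the part of the outcome unrelated to baseline: simulation leaves the full 0.14 SD.

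In the first case the reduction comes from adjusting the remaining children for baseline; it is the same with or without the removed child's baseline. If follow-up is obtained on every removed child, this bias is zero.

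**The case against.** The strongest reply is that the illustration joins two rules. Only the safe-technique rule excludes data, and it need not differ by arm. The rule that could plausibly differ by arm, non-adherence, carries no exclusion. That is correct: the figures show what would happen if non-adherent children were also dropped, and the plan neither says so nor rules it out.

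Second, the order of the draw and the training week is not established. Selection by parental ability could mean screening before the draw, and some figures could not be read. This stands against calling the safe-technique rule a proven exclusion after allocation. It does not touch non-adherence.

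Third, numbers may be small. The plan expects low drop-out and high adherence, calls a parent's failure to learn unlikely, and offers extra training, make-up days and longer walks to recover missed minutes. This limits the likely size of any bias, but it does not supply a data rule.

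Fourth, the lack of an analysis population is partly a missing label, since the text speaks of assigned groups and differences between them. That is fair; taken alone it would be minor.

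A reader might infer that the plan adopts a per-protocol analysis, or that high-intensity results will be inflated. The documents support neither. The written exclusion covers one narrow case, and nothing fixes the number, arm or direction of removals. The remark under Interventions that attention may be harder to hold in the high-intensity group concerns the task and does not predict removals.

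**Conclusion.** The concern holds in a limited form and should be fixed. There is one written exclusion that reads as following allocation, one removal rule that must follow allocation and has no data rule, and no statement that children are analysed as allocated. Bias arises only if removed children are dropped and removals both differ by arm and relate to outcome. Under the assumed one-arm setting at correlation 0.5, it is 0.07 to 0.20 SD for one to three removals, with type I error of 5.5-7.4% for a simple t-test, not the planned repeated-measures analysis. Confidence is medium: the wording is clear, but the order of steps and the number of removals are not.

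**What to change.** 1. Delete the exclusion clause. State that every allocated child is analysed in the allocated group using all available data; results with exclusions may be secondary only.
2. Separate stopping home training, which stays with the PIs, from withdrawal from assessment. Still seek the planned post-intervention, 1-month and 4-month assessments where parents agree, for removals under Methodology and Human Subjects alike. The deletion helps only if follow-up is obtained or the analysis uses baseline.
3. Reconcile Methodology and Human Subjects on the order of selection, draw and training week.
4. Report removals by arm with reasons.

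Settle this before any removal occurs. It costs protocol and SAP wording and a few already planned home visits, with no added recruitment. Some removed families may decline, and part of any bias would then remain.

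Including children who stopped training may dilute the effect. If k of 12 high-intensity children gain nothing over the low-intensity arm (assumed), the effect is multiplied by (12 − k)/12. For k = 1, 2, 3, t-test power at effect size 1.87 goes from 0.992 to 0.980, 0.954 and 0.907. StepWatch power goes from 0.80 to 0.729, 0.646 and 0.557, using the effect size of about 1.20 implied by 80% power at 12 per group. Excluding the same children with the effect unchanged would give 0.781, 0.758 and 0.731 for StepWatch, so part of that loss occurs either way.

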- a diagnosis of a genetic disorder
- cardiac or orthopedic contraindications for standing and walking
- orthopedic surgery in the past 6 months
- use of spasticity-reducing medication or Botox injections in the past 6 months
- participation in other previous or concurrent intensive physical therapy programs

Interventions

All children will continue their regularly scheduled physical therapy during the study period. Frequency of ongoing physical therapy interventions as well as the physical therapy approach will be recorded for each child. All interventions will be conducted at the children's homes. On the first visit, the

PI will provide a portable pediatric treadmill for the family's use at no charge for the duration of the intervention period. The treadmill is designed for research and is equipped with a non-resettable minute timer and adjustable handle bars.²⁷ There will be a one-week training period for each child to familiarize the family with the treadmill intervention. After initial set-up of the treadmill, the PIs will conduct weekly visits to the family. The children will undergo 6 weeks of treadmill training in their homes administered by a parent or primary caregiver who has been trained to safely provide the intervention. The weekly visits will be conducted by the PIs to adjust the treadmill speed and make any needed corrections to the parents'/caregiver's technique.

Children assigned to the high-intensity group will walk on the treadmill 5 days/week, twice daily for 10-20 min for 6 weeks. Children in the low-intensity group will walk on the treadmill 2 days/week, once daily for 10-20 minutes for 6 weeks. The parents will be encouraged to take a break on two days of their choice, depending on the family's other commitments. The treadmill speed will be determined based on previous protocols developed by [name].¹⁷ The initial treadmill speed will be set at the maximum speed at which the child can maintain walking without dragging his/her feet for more than 3 seconds. The treadmill speed will be increased during the weekly investigator visits as tolerated by the child, using the same criterion. The children will wear shoes and/or their customary orthotics during the walking. The treadmill speeds will not exceed 0.6 meters/second, which is the maximal speed available on the pediatric treadmills. It is anticipated that all children will walk at a speed between 0.1 and 0.3 meters/second.

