Outcome measures at the *activity level* of the International Classification of Functioning, Disability and Health (ICF) Model will include the Gross Motor Function Measure (GMFM), Peabody Developmental Motor Scales-2 (PDMS-2), Functional Mobility Scale (FMS), the Timed 10-meter Walk Test, the 1-minute Walk Test and the StepWatch accelerometer. Outcome measures at the *participation level* of the ICF Model will be the Pediatric Evaluation of Disability Inventory Caregiver Mobility Scale (PEDI). Videotapes of assessments will be scored by an assessor blinded to group allocation for the GMFM and PDMS-2. StepWatch data will be collected for all awake daytime hours over a 7 day period at study onset before treadmill training commences and at each of the post-intervention assessments. The StepWatch monitor will be secured around the child's ankle with a small knit cuff. [name] has successfully employed this method of monitor attachment in toddlers with and without motor limitations.^{23,36} StepWatch outcomes will be average number of strides/day and the percentage of the time walking.

[figure not shown]
In order to address specific aim # 1 (optimal parameters for dosing home-based treadmill training by comparing high-intensity to low-intensity treadmill training) and specific aim # 2 (effects of high- versus low-intensity treadmill training on walking attainment and overall walking activity), between-group differences of all the outcome measures will be analyzed as described in the next section. Specifically, between-group differences in GMFM and PDMS-2 will examine the effects of dosage on walking attainment and skills related to standing and walking. The changes in support needed for walking will be measured by the FMS in the two groups. Differences in walking speed and walking endurance will be analyzed using the data from the Timed 10-meter Walk Test and the 1-minute Walk Test, respectively. The parent perspective on overall child mobility will be analyzed by using the PEDI. Finally, overall walking activity will be shown by between-group differences from the StepWatch data.

Data Analysis

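### Aim 1 promises an optimal dose, but two bundled regimens can show only which does better, and the tests named for StepWatch, PEDI and FMS do not deliver that between-arm comparison

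*Combined protocol and SAP*

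**What the plan says.** All places are in the combined protocol and SAP.

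- **Aims (Methodology, just before Data Analysis).** The first aim is "specific aim # 1 (optimal parameters for dosing home-based treadmill training by comparing high-intensity to low-intensity treadmill training". The second is "specific aim # 2 (effects of high- versus low-intensity treadmill training on walking attainment and overall walking activity". The same paragraph commits to between-group differences on all outcome measures.
- **Power Analysis.** The PDMS-2 calculation is introduced as serving the question of optimal dosing. The StepWatch paragraph opens "To assure sufficient power to assess the effects of treadmill training on overall walking activity" and then states that "12 per group would have 80% power to detect a 3000 stride/day difference in treatment intensity as measured with the StepWatch monitor".
- **Regimens (Interventions, repeated in Methodology).** For the more intensive arm the plan reads: "Children assigned to the high-intensity group will walk on the treadmill 5 days/week, twice daily for 10-20 min for 6 weeks". The other arm has fewer days and a single daily walk, with the same session length and number of weeks. The rule for setting and raising speed is the same in both arms.
- **Arms (Enrollment procedures).** "twelve children will receive high-intensity treadmill training and twelve children will receive low-intensity treadmill training". There is no untrained arm, and the Interventions section keeps every child on usual physical therapy.
- **Data Analysis.** Repeated-measures ANOVA is named for PDMS-2, GMFM and the two walk tests, the Friedman test for PEDI and FMS, and a Wilcoxon signed-rank test for paired data for StepWatch. Whether children reached a minimum clinically important change will be reported for the GMFM. No effect estimate or confidence interval is specified.

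**The concern.** There are two separate problems.

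The first is what aim 1 can deliver. An optimum is a statement about a range of doses, and optimal parameters is a statement about the separate components of dose. The trial observes two packages in which both components move together. A conclusion worded to match the aim would go beyond the data, whichever arm did better.

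The second is what the named tests estimate. The strength of the trial is the randomised difference between arms. For three outcomes the plan names tests built for repeated measurements on the same child. In children under 3 who continue therapy and are followed for 26 weeks, change over time mixes training, development and therapy, and no arm exists to separate them. If those tests are run as named, StepWatch, PEDI and FMS could be reported without the comparison that the randomisation was set up to provide.

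**Working it through.** **1. The plan's own sample size.** Inputs: standardised effect 1.87 and power 0.95 (Fig. 4 caption), and alpha 0.05 (Data Analysis), taken as two-sided because sidedness is not stated. A two-sample t-test (noncentral t) needs 8.53, so 9 per arm and 18 in total; power at 9 per arm is 96.1%. The stated 18 reproduces. It is the sample size for a single two-group contrast.

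**2. Planned dose.**

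| | High | Low | Ratio |
|---|---|---|---|
| Days/week | 5 | 2 | 2.5 |
| Sessions/day | 2 | 1 | 2 |
| Sessions/week | 5 × 2 = 10 | 2 × 1 = 2 | 2.5 × 2 = 5 |
| Sessions in 6 weeks | 60 | 12 | 5 |
| Minutes/week at 10–20 min each | 100–200 | 20–40 | 5 at equal session length |
| Minutes in 6 weeks | 600–1200 | 120–240 | 5 at equal session length |

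At opposite extremes of session length the ratio runs from 100/40 = 2.5 to 200/20 = 10. No planned exposure lies between 40 and 100 minutes per week.

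**3. What one contrast can identify.** Crossing days per week (5 or 2) with sessions per day (2 or 1) gives four cells. The trial fills two: (5, 2) and (2, 1). Even a model with no interaction has three unknowns (an intercept, a days effect and a sessions effect), and there are two arm means. The arm difference equals the days effect plus the sessions effect, and any split of that sum fits equally well. Likewise, the simplest curve with an interior optimum, a quadratic in total dose, has three coefficients and needs at least three dose levels. No third dose, factorial structure or dose-response analysis is described.

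**4. The named tests against the promised comparison.**

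- *StepWatch.* A signed-rank test needs pairs. Enrollment procedures and Methodology describe allocation by drawing, four children to each arm per site, with no matching of individual children. The only natural pairs are visits of the same child, so the test addresses change within a child.
- *PEDI and FMS.* The Friedman test compares repeated measurements within blocks. With the child as block and visits as conditions, it tests change over time and has no term for independent groups, although the plan says it is for comparison between groups.
- *The powered StepWatch contrast.* The stated 80% power with 12 per arm is for a difference between intensities. By a two-sample t-test it implies a standardised difference of 1.20, so an SD of 3000/1.197 ≈ 2,507 strides/day. The SD is not given, so the figure cannot be verified. Either way, the powered contrast is between arms and the named test is not.

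**The case against.** **Aim 1 states its own scope.** It says the aim is met by comparing high with low intensity, and no text says the report will name an optimal dose. Fuller aims may also exist elsewhere: the first numbered figure here is Fig. 4, which suggests that background text is not in view. This is fair. It means the error is in the claim and not in the design. But the wording stands in the document that carries the analysis plan, and it recurs in the Power Analysis.

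**Delivered dose is recorded.** Parents log minutes and speed for each walk (Methodology), so a dose-response analysis is possible. None is planned, however, and minutes walked within an arm are not randomised; they may reflect tolerance and progress.

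**The test choice may be a slip.** The intention is clearly between-group for PEDI and FMS, and for every outcome in the Methodology. That supports the fix, but the tests as named still do not carry it out.

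**Stronger readings that the documents do not support.** A reader might infer from "To assure sufficient power to assess the effects of treadmill training on overall walking activity" that the trial plans to claim an effect of training against none. The same sentence defines the contrast as a difference in treatment intensity, and aim 2 is worded as high versus low. This is loose wording. A reader might also fear that a non-significant result would be presented as showing that the lower dose suffices. No equivalence or non-inferiority claim appears anywhere, so that remains hypothetical. Precision does not make the case either. The unadjusted 95% half-width with 12 per arm is t(22, 0.975) × √(2/12) = 2.074 × 0.408 = 0.85 SD, but this is true of any 12-versus-12 comparison of means and says nothing specific to dosing.

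**Conclusion.** The point holds in two parts.

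- **Aim 1.** The design gives one contrast between packages of 60 and 12 planned sessions. It can show whether one does better than the other. It cannot locate an optimum or divide a difference between days per week and sessions per day. This follows from the number of arms and would not change with a larger sample.
- **Three outcomes.** The tests named for StepWatch, PEDI and FMS address change within children, which cannot be attributed to treadmill training here, and they conflict with the between-group differences promised in the Methodology. This assumes that the pairs or blocks are visits of the same child, the only natural reading because no matching is described.

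Nothing here invalidates the randomised comparison or the stated sample size of 18, and it implies nothing about which regimen is preferable. It is a correction to make before analysis.

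**What to change.** 1. Reword aim 1, and the matching phrase in the Power Analysis, as a comparison of two regimens: whether outcomes differ between training 5 days/week twice daily and training 2 days/week once daily. Drop the word optimal, and state that the components of dose cannot be separated.
2. In Data Analysis, make the between-arm difference with a 95% CI the reported result for every outcome. For StepWatch and PEDI, one option is the change from baseline compared by rank-sum test, with a Hodges–Lehmann difference and its interval. For the ordinal FMS, the probability that a child in one arm scores better than a child in the other, with its interval, would serve.
3. Label all within-arm change as descriptive, including the counts of children reaching the GMFM minimum change. Show those counts by arm. The paired and Friedman tests may stay only under that label.
4. Align the opening phrase of the StepWatch power sentence with the treatment-intensity contrast that the sentence goes on to define.

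The cost is an amendment to the wording, re-specification of the tests for three outcomes, and confidence intervals in the tables. No arm, child, visit or regimen changes. The downside is a narrower claim.
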